MedDRA Medical Dictionary for Regulatory Activities

N/A Not Applicable

NIS Non-Interventional Study

NNH Number Needed to Harm

NO Nitric oxide

NT-proBNP N-terminal pro-brain natriuretic peptide

NYHA functional New York Heart Association functional class

class

OM Operating manual

PAH Pulmonary arterial hypertension

PAS Post-Authorization Study

PASS Post-Authorization Safety Study

PEA Pulmonary endarterectomy

PH Pulmonary hypertension

PSUR Periodic Safety Update Report

QPPV Qualified Person Responsible For Pharmacovigilance

QRP Quality Review Plan

SAE Serious Adverse Event

SAP Statistical Analysis Plan

STROBE Strengthening the Reporting of Observational Studies in Epidemiology

WHO DD World Health Organization Drug Dictionary

WHO FC World Health Organization Functional Class

6-MWT Six minute walk test

3 Responsible parties

3.2 Collaborators / Committees

See list of stand-alone documents section Annex1

4 Abstract

Acronym / Title	EXPERT, EXPosurE Registry RiociguaT in patients with pulmonary hypertension		
Protocol version identifier	Version 1		
Date of last version of protocol	28 th Jan 2014		
IMPACT study number	16657		
Study type	□ non-PASS □ PASS Joint PASS: □ YES □NO		
Author	[name] PhD		
Rationale and background	PAH and CTEPH are rare and life-threatening diseases. Adempas® has shown to be effective and well tolerated in both indications in two randomized controlled trials. Adempas® is the first member of a new class of drugs, the sGC-stimulators (soluble guanylate cyclase-stimulators) and the first drug ever having shown efficacy in CTEPH. In accordance with the regulatory requirements this registry has been designed to collect information about the long-term safety of Adempas® in real clinical practice outside the regulated environment of a controlled clinical study.		
Research question and objectives	The primary objective is the assessment of long-term safety of Adempas® in real life clinical practice.		
	In addition it is going to prospectively collect data on clinical effectiveness, resource use, and how Adempas® is used by PH experts under real-life conditions.		
Study design	The EXPERT registry is a global, multicenter, prospective, uncontrolled, non-interventional cohort study documenting data from patients with PH treated with Adempas®.		
Population	Patients who have been prescribed Adempas [®] for a medically appropriate use will be eligible to be included into this registry. Indications and contraindications according to the local market authorization should be considered.		

Variables	Adverse and serious adverse events will be captured as well as all-cause mortality. Extra space will be provided for the documentation of symptomatic hypotension, hemoptysis and pulmonary haemorrhage as events of special interest. In addition relevant information on medical history, concomitant conditions and medication, resource use and clinical effectiveness will be captured.		
Data sources	The investigator is requested to collect historic data (demographic and clinical characteristics) from medical records, and to collect treatment related data during visits that take place in routine clinical practice.		
Study size	It is planned to enroll 900 patients with the aim to include a significant proportion of patients newly starting Adempas® treatment. This sample size allows detecting at least three "uncommon" AEs (with a probability of 83%) with an incidence of 0.5% (5/1000) or more.		
Data analysis	All background variables and outcome parameters will be analyzed descriptively with appropriate statistical methods: categorical variables by frequency tables (absolute and relative frequencies) and continuous variables by summary statistics (i.e. mean, standard deviation, minimum, median, quartiles and maximum). Continuous variables will be described by absolute value and as change from baseline per analysis time point, if applicable.		
	All analyses will be performed for the total study population (overall analysis) and separately for PH subtype, patients who newly started or have already been on Adempas®, countries or regions if applicable and if patient numbers are sufficient, and in patients receiving at least one dose of Adempas®. All statistical details will be described in the Statistical Analysis Plan (SAP). It is planned to have yearly interim analyses on primary and secondary endpoints for the purpose of the PSUR and a final analysis after end of the study.		
Milestones	Start of data collection will be in April 2014 after official EMA approval with inclusion of the first patient (FPFV). With a recruitment period of 3 years and an observation period of 1-4 years LPLV is planned for April 2018.		

5 Amendments and updates

NA

6 Milestones

Definitions:

• Start of study: first center initiated

• Start of data collection: date of first data entry in database (prospective studies usually: FPFV;

retrospective studies: start of data entry)

• End of data collection: date of last data entry in database (usually after LPLV)

• End of study: database close

• Observation period: time-window for data collection (usually FPFV to LPLV)

• Final report: Final report of study results 12 months after database close

Table 1 presents planned milestones for the project. These milestones are based on a timely review and approval of the project. Administrative changes to milestones due to delays in study preparation and enrolment do not require amendments to the protocol.

Table 1: Milestones

Milestone	Planned date
Registration in the EU PAS register	Mar 2014
Start of data collection	Apr 2014
End of data collection	Apr 2018
Final report of study results	Aug 2018

7 Introduction: Background and Rationale

Pulmonary Arterial Hypertension (PAH) is a rare, progressive and life-threatening disease. It is characterized by a chronic increase in pulmonary vascular resistance (PVR) due to progressive vascular remodeling that can ultimately lead to right heart failure and death [1] [2]. Symptoms of PAH are related to right heart failure and include exercise-induced dyspnea, exhaustion, leg edema and decreased quality of life. In untreated patients with idiopathic PAH the life expectancy is reduced to 2.8 years after diagnosis, whereas in contemporary registries in the era of modern PAH-specific treatments the survival rates have increased to 83% and 58% at 1 and 3 years respectively [3] [4]. The incidence is currently estimated as 2.4 cases per million adult inhabitants per year with a prevalence of 15 cases per million adult inhabitants [5]. Available PAH-specific treatments include prostacyclin analogues, endothelin receptor antagonists, and PDE5-inhibitors. The available drugs predominantly act as vasodilators and improve exercise capacity [6]. Despite advances in the clinical management

based on these available therapies for PAH, there is still significant unmet medical need for improvement as the mortality of patients with PAH remains high (15% at 1 year and 32% at 3 years) [7].

Chronic Thromboembolic Pulmonary Hypertension (CTEPH) is a different progressive and life-threatening type of pulmonary hypertension. Whereas symptoms as well as epidemiology of CTEPH are similar compared with PAH, there are significant differences regarding aetiology, diagnosis and treatment [8] [9]. In CTEPH the increase in pulmonary vascular resistance is a result of a pulmonary artery obstruction by residual organized thrombi [10]. A ventilation-perfusion-scan is important for differential diagnosis as a normal scan excludes CTEPH [11]. The standard and potentially curative treatment for CTEPH is pulmonary endarterectomy (PEA). However 20 to 40 % of patients are not eligible for surgery and in 10-15% of patients PH may persist or reoccur after surgery [12] [13] [14] [15]. Specific PAH drugs had failed in the past to show efficacy in inoperable CTEPH and before Adempas® no drug treatment has been approved for these patients [16].

Adempas[®] is the first member of a new class of drugs, the sGC-stimulators (soluble guanylate cyclase-stimulators). It restores the NO-sGC-cGMP pathway and leads to increased generation of cyclic guanosine monophosphate (cGMP) which plays an important role in regulating vascular tone, proliferation, fibrosis, and inflammation. Adempas[®] directly stimulates sGC independently of nitric oxide (NO), while also increasing the sensitivity of sGC to NO. This appears to be of importance as pulmonary hypertension (PH) is associated with pulmonary endothelial dysfunction and can be related to low levels of NO [17] [18] [19] [20] [21].

Adempas® is the first drug that could demonstrate robust efficacy in two placebo-controlled, multicentre trials in two different indications of pulmonary hypertension (PH). In the CHEST-1 study Adempas® showed for the first time robust clinical efficacy in patients with inoperable chronic thromboembolic pulmonary hypertension (CTEPH) and in patients with persistent CTEPH after surgery by significantly improving exercise capacity as well as relevant secondary endpoints such as hemodynamics and WHO functional class. In the PATENT-1 study in pulmonary arterial hypertension (PAH) Adempas® could for the first time show significant improvement in exercise capacity in treatment-naïve patients as well as in patients pre-treated with endothelin receptor antagonists (ERAs) or non-intravenous prostacyclin analogues. At the same time a consistent significant improvement across the secondary endpoints including hemodynamics, WHO functional class and time to clinical worsening could be demonstrated. In both studies Adempas® was well tolerated with a good safety profile [22] [23].

EXPERT is a global, multicenter, prospective, uncontrolled, non-interventional study documenting data from patients with PH treated with Adempas[®]. The objective of the registry is to monitor the long-term safety of Adempas[®] under clinical practice conditions outside the regulated environment of a controlled clinical study. In addition the registry offers a structured prospective collection of data on the clinical effect, resource use, and how Adempas[®] is used by PH experts.

In accordance with guidance from the 5th World Symposium on Pulmonary Hypertension and the European Union Committee of Experts on Rare Diseases on the future setup of registries, EXPERT will be linked with COMPERA, one of the largest global academic PH registries, instead of creating another drug registry in this rare disease area.

With currently more than 4800 PH patients, COMPERA is the largest global academic databases in PH, characterised by high data quality and low loss to follow up [24] COMPERA captures the relevant

demographic and clinical data on PH. Although COMPERA is predominantly present in Europe, there are no geographical restrictions.

COMPERA will be the technical and data platform for EXPERT. Data will be captured according to the COMPERA core CRF and Adempas®-specific data and more detailed safety documentation will be added.

EXPERT will be an Adempas® exposure registry and participating investigators will have contracts with Bayer separate from COMPERA. The specific reporting requirements of a post-approval safety study will be specified in the contract. Bayer will have exclusive access to the data captured specifically for Adempas®. The requirements for safety data reporting will be fulfilled. Data documented for EXPERT according to the information in the COMPERA standard CRF will be available and accessible in the COMPERA registry. A center participating in EXPERT may object to have the data documented in COMPERA (opt-out option).

Alignment of data documentation and format will be discussed that could enable an exchange and comparability of data on Adempas® use from other academic national registry e.g. with the French National Registry.

8 Research questions and objectives

8.1 Primary objective

The primary objective is the assessment of long-term safety of Adempas® in real life clinical practice.

8.2 Secondary objective(s)

The secondary objective(s) in this study is/are:

- Long-term safety of Adempas® in the different PH indications (PAH, CTEPH)
- Effectiveness of Adempas® in the long-term follow-up of PH patients
- Information on resource use
- Information on how Adempas® is used (e.g. indication and indication subgroups, dose)

9 Research methods

9.1 Study design

The EXPERT registry is a global, multicenter, prospective, uncontrolled, non-interventional cohort study documenting data from patients with PH treated with Adempas[®]. It is linked with the existing global COMPERA registry, a global academic multicenter prospective registry, which documents consecutive patients with the different forms of pulmonary hypertension (PH) treated with specific PAH drugs. For EXPERT the documentation in COMPERA will be extended to include additional Adempas[®]-specific data.

It is planned to include around 35 countries in the region Europe, Asia Pacific, Latin America.

The study will start after Adempas[®] has been authorized and made commercially available in the countries involved in the study.

All patients prescribed with Adempas[®] for a medically appropriate use, consent to participate, and fulfil the selection criteria are eligible for enrolment into the study. Patients will be followed up for an observation period of 1 up to 4 years (recruitment period 3 years). Patient's clinical information will be documented at time of the initial visit and approximately every three to six months according to local clinical practice thereafter. Data collection will continue until 30 days after the end of Adempas[®] therapy.

The decision on clinical management of the patient including the actual treatment duration will be determined solely by the physician.

The study ends 12 months after enrolment of the last patient

Serious adverse events will be followed up until resolution.

9.1.1 Primary endpoint(s)

The primary endpoints are:

- Incidence of adverse events/ serious adverse events
- Incidence of all-cause mortality

9.1.2 Secondary endpoint(s)

The secondary endpoints are:

Safety

- Incidence of AE and SAE in the different PH indications (PAH, CTEPH)
- Incidence of AE of interest overall and in the different PH indications (PAH, CTEPH)

Effectiveness

• Clinical effect in the follow-up of PH patients

Resource use

- Hospitalization / outpatient visits
- Administration and any change in drug treatment for PH

9.1.3 Strengths of study design

In this rare disease area a multinational exposure registry provides the ideal setting to monitor long-term drug safety and clinical effect in real clinical practice. This setting with a larger patient number than in regulated controlled clinical studies allows for a structured prospective documentation of long-term data on safety, clinical effect, and information on how Adempas® is used by PH experts. As Adempas® is the first sGC-stimulator in clinical use and all available clinical data derive from well-defined clinical studies, this registry may collect additional data on important potential safety risks, drug interactions and missing information.

The link with an existing, large and well established pulmonary hypertension registry is expected to enhance acceptance and facilitate patient recruitment for the study.

9.2 Setting

9.2.1 Eligibility

Patients who have been prescribed Adempas[®] for a medically appropriate use will be eligible to be included into this registry. Indications and contraindications according to the local market authorization should carefully be considered.

9.2.2 Inclusion criterion/criteria

- Female and male patients who start or are on treatment with Adempas®
- Written informed consent

9.2.3 Exclusion criterion/criteria

Patients currently participating in an interventional clinical trial

9.2.4 Withdrawal

Each patient has the right to refuse further participation in the study at any time and without providing any reasons. A patient's participation is to be terminated immediately upon his/her request. The investigator should seek to obtain the reason and record this on the Case Report Form (CRF).

In this non-interventional study, withdrawal from the study is independent of the underlying therapy. On the other hand, the follow-up documentation will continue until 30 days after end of therapy.

9.2.5 Replacement

Patients will not be replaced after drop out.

9.2.6 Representativeness

Source population of the present study are patients with pulmonary hypertension, primarily PAH and CTEPH. Patients with this rare condition are mostly diagnosed and managed in specialized centers. This includes the initiation and any change of specific drug therapy. The participation of these specialized centers into the registry, the consecutive recruiting of patients and the broad definition of selection criteria is going to ensure the representativeness of the study population.

9.2.7 Visits

Due to the observational trial design, the study protocol does not define exact dates of the follow-up visits. Data are only collected on assessments that are performed by the site routinely as per local standards of care.

The investigator documents an initial visit, follow-up visits and a final visit for each patient in the case report form (CRF). Follow-up visits in clinical routine usually take place every 3 to 6 months. The CRF will allow for the documentation of visits as performed according to the management of the individual patient.

The final visit is meant to document the end of observation.

Patients will be followed up for an observation period of 1 up to 4 years (recruitment period 3 years) or until 30 days after end of Adempas® treatment.

Enrollment / Initial visit

Once a patient is found eligible for inclusion, the investigator will inform the patient about the study. Where applicable, this will include discussing the consent form and asking the patient to read and – when agreeing to participate – sign the informed consent.

- Following information will be collected (details in section 9.3) Patient Demographics
- Medical history
- Comorbidity
- Adverse events
- PH etiology according to Dana Point Classification 2008 and disease history
- Pregnancy
- History of smoking
- 6-minute walking distance
- NYHA/ WHO FC
- Borg dyspnoea index
- EQ5D VAS,
- Lung Function, Cardiac rhythm,
- Haemodynamic parameters from right heart catheter measurement
- Biomarkers (NTproBNP, BNP)
- Laboratory tests
- Treatment:
 - Relevant prior and concomitant medication
 - PAH-specific drugs or Adempas[®]
 - o Systemic BP before start of Adempas®
- Resource use

Follow-up visits during treatment

Follow-up examinations in clinical routine usually take place every 3 to 6 months. The CRF will allow for visits to be documented according to the management of the individual patient. At each of these visits the following will be documented:

- Adverse events
- · Changes of treatment
- · Changes regarding demographics, pregnancy, smoking
- 6-minute walking distance
- NYHA/ WHO FC
- Borg dyspnoea index

- EQ5D VAS,
- Lung Function, Cardiac rhythm,
- Haemodynamic parameters from right heart catheter measurement
- Biomarkers (NTproBNP, BNP)
- Laboratory tests
- Resource use

Final visit and end of observation period

The final data collection (last visit) is 30 days after discontinuation of therapy or at end of study (whatever is earlier). At this final observation point, the patient's condition and a treatment assessment will be documented as at the follow-up visit with the additional information on:

- regular end of observation, or
- discontinuation of therapy
- reason for discontinuation, i.e.: patient failed to follow up, patient decision, investigator decision, pregnancy, insufficient / no treatment effect, unexpected strong treatment effect, (suspected) drug interaction, SAE (must be reported immediately!), death (date and relation to disease or treatment), therapy change (which therapy and reason for switch), centre closed, study termination

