9.3.16 Prior and concomitant medication

All medication taken before study start (initiated and stopped before study start) is termed prior medication. All medication taken in addition (either initiated before study start or during the study) is termed concomitant medication.

Prior and concomitant medication meeting the criteria listed below are considered to be relevant and have to be documented:

- PH/PAH-specific therapy
 - o Adempas®
 - o ERA: bosentan, sitaxsentan, ambrisentan, macitentan
 - o PDE-5 inhibitors: sildenafil or tadalafil (physician will be alerted that the combination of PDE5 inhibitors with Adempas® is contraindicated)
 - prostacyclins
 - epoprostenol (Flolan)
 - treprostinil
 - iloprost
 - beraprost
 - o tyrosine kinase inhibitor: imatinib
 - o other specific targeted therapy: calcium channel blocker, other
 - o oral anticoagulation
 - Vitamin K antagonists
 - other
- other medications (only CHD: other cardiovascular drugs, antiplatelets)

Information to be documented includes:

- Trade name and INN
- Start and stop date
- Date of, dose, date of switch or addition of a specific drug/ Adempas®
- Reason for change (lack of efficacy or tolerability, patient's request, administrative)
- Dose
- Unit
- Frequency
- Administration mode
- Indication

Additional information on Adempas® to be documented includes:

- Individual dose after initial dose adjustment period
- BP before the 1st administration

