9.7.4 Analysis of secondary outcome(s)

The secondary safety outcomes will be analyzed similar to the primary outcomes. Subgroup analyses will be conducted for selected secondary endpoints (e.g. 6 Minutes Walking Test, NYHA/WHO FC, hospitalization).

Analyses of adverse events will be conducted for PH subgroups (inoperable vs. post- surgery CTEPH patients, monotherapy vs. combination therapy PAH patients) .

Adverse events of interest will be analysed in detail. Adverse events of interest are

- Symptomatic hypotension
- Hemoptysis/ pulmonary haemorrhage

Further analyses of information on adverse events of interest as given by the detailed questionnaire and the AE page will be evaluated.

Kaplan Meier plots will describe the time until the individual events of interests

For the effectiveness variables summary statistics and changes form baseline will be calculated for

- 6 Minutes Walking Test,
- Borg Dyspnoea Index
- EO5D VAS
- Hemodynamic measurements
- Biomarkers

NYHA/WHO FC will be analyzed by frequency tables including changes from baseline.

The variables of hospitalization due to PH and drug utilization (reason and drug switch or interruption or discontinuation of Adempas®) will be analyzed by frequency tables and summary statistics.

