11.2 Collection

Starting with the first application of Adempas® all non-serious adverse events (AE) must be documented on the AE Report Form or in the CRF / EDC system and forwarded to the sponsor within 7 calendar days of awareness. All serious AEs (SAE) must be documented and forwarded immediately (within 24 hours of awareness). For each AE, the investigator must assess and document the seriousness, duration, relationship to study drug, action taken and outcome of the event.

If a pregnancy occurs during the study, although it is not a serious adverse event, it should be reported within the same time limits as a serious adverse event. The outcome of a pregnancy should be followed up carefully and any abnormal result of the mother or baby should be reported.

The documentation of any AE/SAE ends with the completion of the observation period of the patient. However, any AE/SAE occurring up to 30 days after the last intake of Adempas® has to be documented, even if this period goes beyond the end of observation.

As long as the patient has not received any Adempas[®], AEs /SAEs do not need to be documented as such in this non-interventional study. However, they are part of the patient's medical history.

For any serious drug-related AE occurring after study end, the standard procedures that are in place for spontaneous reporting have to be followed.

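### The final-visit list of discontinuation reasons has no entry for a non-serious adverse event and mixes drug stops with ends of observation, so a table built on it could misclassify both

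*Protocol*

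**What the plan says.** The closing part of Protocol 9.2.7 has the final visit record either "regular end of observation, or" discontinuation of therapy. For the latter it asks for a "reason for discontinuation, i.e.: patient failed to follow up, patient decision, investigator decision, pregnancy, insufficient / no treatment effect". The list goes on with "unexpected strong treatment effect, (suspected) drug interaction, SAE (must be reported immediately", then death, and ends with "therapy change (which therapy and reason for switch), centre closed, study termination".

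Two other records bear on why the drug was stopped:

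- **Medication record (9.3.16).** Adempas is among the drugs documented. The record takes "Start and stop date" and "Reason for change (lack of efficacy or tolerability", followed by the patient's request and administrative reasons.
- **Adverse-event record (11.2).** "For each AE, the investigator must assess and document the seriousness, duration, relationship to study drug, action taken and outcome of the event". This applies to serious and non-serious events alike.

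Section 9.3.2 makes discontinuation of Adempas, with its reason, a secondary variable under resource use. Section 9.7.4 plans frequency tables and summary statistics for "drug utilization (reason and drug switch or interruption or discontinuation of" Adempas. Section 9.2.4 states that withdrawal from the study does not depend on the underlying therapy.

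**The concern.** The list is introduced by *i.e.*, so it reads as complete rather than as examples. A patient who stops because of non-serious symptomatic hypotension, which the protocol names as an event of interest, has no entry that says so. A patient still taking the drug when contact is lost or the centre closes did not reach a regular end of observation. The form then offers only discontinuation of therapy.

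The registry's primary objective is long-term safety, and readers will take the table of reasons for stopping as a tolerability result. If it rests on this list, the row for adverse events can be too small, the rows for patient or investigator decision too large, and the total number of discontinuations too high. A reason coded wrongly during data collection is hard to put right later.

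**Working it through.** The protocol states no figure for discontinuation, so there is none to reproduce on this point. Its one size calculation (9.5: 900 patients, incidence 0.5%, at least three cases, 83%) reproduces at 0.8271 by the exact binomial. Only the 900 is used below.

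**Step 1. Where each situation lands in the three records.**

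| Situation | Final-visit list (9.2.7) | Medication record (9.3.16) | AE record (11.2) |
|---|---|---|---|
| Stop for a serious AE | SAE | tolerability, printed jointly with efficacy | action taken |
| Stop for a non-serious AE | no entry of its own; patient decision, investigator decision, unexpectedly strong effect or therapy change | as above | action taken |
| Stop for lack of effect | own entry | printed jointly with tolerability | not needed |
| Still on drug, contact lost or centre closed | listed as a reason for discontinuing | drug not stopped, so no stop date arises | nothing to record |

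The second row shows the missing category, and that the AE record can still identify the stop. The fourth row shows the mixing of two endings. The AE record cannot repair that, though a missing stop date in the medication record may reveal it.

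**Step 2. Do the two reason lists agree?** No. Section 9.2.7 separates insufficient effect from SAE and has no tolerability entry. Section 9.3.16 names tolerability, with no condition on seriousness, but prints it in one phrase with lack of efficacy. Whether that phrase is one response option or two depends on the CRF.

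**Step 3. Which record feeds the table in 9.7.4?** The protocol does not say, and it gives no rule for conflicts between records.

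**Step 4. Illustration on assumptions only.** Let *t* be the proportion of the 900 who stop for any adverse event, *s* the share of those events that are non-serious, and *c* the share of non-serious stops recovered from the other records. The number visible as adverse-event stops is

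900 × *t* × [1 − *s* × (1 − *c*)].

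None of *t*, *s* and *c* is in the protocol.

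| *t* | true stops | *c* = 0, *s* = 25% | *c* = 0, *s* = 50% | *c* = 0, *s* = 75% | *c* = 1 |
|---|---|---|---|---|---|
| 5% | 45 | 33.75 | 22.5 | 11.25 | 45 |
| 10% | 90 | 67.5 | 45 | 22.5 | 90 |
| 15% | 135 | 101.25 | 67.5 | 33.75 | 135 |

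For example, 900 × 0.10 × (1 − 0.50) = 45 of 90. With full recovery from the other records nothing is lost. The result therefore runs from no error to a large one, depending on a source the protocol does not name.

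**The case against.** The strongest reply is that the information is collected elsewhere. Action taken is required for every adverse event, and the medication record names tolerability, so a stop for a non-serious event can be derived from two other places. Section 9.7.4 does not say that the final-visit list is the source. Its table also covers interruptions, which that list does not record, so the list can hardly be the only source. This stands. A reader might infer that discontinuation for intolerance will be under-counted; the protocol does not support that.

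A reader might also infer that a non-serious stop can only be coded as somebody's decision. That goes too far. The entry for an unexpectedly strong effect could hold some cases of hypotension, and therapy change carries its own reason. Neither, however, identifies an adverse event as the reason.

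It can further be said that the administrative endings are labelled, so an analyst can exclude them. That is true of loss to follow-up, centre closure and study termination. It does not help with patient decision, which may mean leaving the registry or stopping the drug.

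Finally, exact response options belong to the CRF and table derivations to the SAP. Neither is shown, and either may settle the matter. Even so, the protocol itself fixes a list that disagrees with its own Sections 9.2.4 and 9.3.16.

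**Conclusion.** The point holds in a limited form. The final-visit list lacks an entry for a non-serious adverse event or intolerance, places ends of observation under discontinuation of therapy, and does not match the list in 9.3.16. If the table in 9.7.4 is drawn from it, non-serious adverse-event stops can be dispersed over other categories, and patients still on drug can be counted as having stopped.

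The size cannot be computed from the protocol; the counts under working rest on assumed rates and are not estimates. The effect is confined to a descriptive secondary variable. The primary endpoints (adverse events, serious adverse events and all-cause mortality, analysed under 9.7.3) are counted from their own records and do not use this list. Discontinuation due to adverse events is not itself a named endpoint. The change is still worth making, because it is specific and nearly free while the CRF has not been issued; Annex 1 dates the CRF to when the first country is ready to enrol.

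**What to change.** These changes concern data capture and analysis only.

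1. In 9.2.7, replace the SAE entry with adverse event, marked serious or non-serious. Immediate reporting of SAEs stays as it is.
2. Record the reason for end of Adempas treatment in one field and the reason for end of observation in another. Loss to follow-up, centre closure, study termination and withdrawal of consent belong in the second.
3. In 9.3.16, list lack of efficacy and tolerability as separate reasons, so that the two lists agree.
4. In 9.7.4, state that the count of discontinuations due to adverse events comes from the action-taken field of 11.2, reconciled with the reason field. Section 11.1 lets lack of drug effect count as an adverse event, so the reconciliation should say in which row such stops appear.

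The cost is a few CRF response options, some wording and one reconciliation check. No visit or assessment is added.
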